9.1.1. Enrollment

All subjects and the parent(s)/legal guardian need to provide their informed consent/assent in accordance with the informed consent/assent regulations per geographic region. If the subject agrees to participate in the study, he/she and/or the parent/legal guardian will be asked to sign the informed consent form (ICF)/Assent form (as applicable). Once the ICF/Assent forms are signed, a copy of the signed ICF/Assent forms will be provided to the parent/legal guardian and/or the subject. The Informed Consent and Assent forms are provided separate from this CIP.

The subject and/or parent or legal guardian must sign the ICF/Assent prior to performing any study specific procedure. A subject is considered enrolled in this study at the time the subject and/or parent/legal guardian signs the ICF/Assent form. The subject will be assigned a unique, sequential code linked to their name, alternative subject identification or contact information. The investigator will maintain a log of all subjects enrolled (enrollment log) in the study. The total enrollment for the study is 10 treated subjects.

9.1.2. Pre-op

The following information will be collected at the preoperative visit:

- Verification of Inclusion/Exclusion criteria
- Demographics
- Medical History
- Physical Assessment (weight and height)
- Imaging (PA, lateral, lateral bending, and left-hand X-rays, MRI)
- Radiographic assessments as per standard of care
- PedsQL
- SRS-22
- Neurological Status
- Pulmonary Function (Spirometry)
- Pregnancy test (administered to all female subjects of child-bearing potential within 72 hours prior to surgery)
- Adverse Events
- Study Deviations

9.1.3. Surgery

The surgery procedure should occur as soon as possible after the eligibility report has been received from the imaging vendor but no later than 3 months after the date of acquiring the X-ray images. If the images cannot be done within the required window, new images should be obtained.

The following information should be collected during surgery:

- Surgery procedure data
- Surgery Time
- Blood loss and Transfusion
- Device information
- Adverse Events and/or device deficiencies
- Study Deviations
- StealthStation Images (only collected at study sites using image guidance – standard of care images)
- Intraoperative images (only collected at study sites not using image guidance – standard of care images)

It is recognized that a subject might be enrolled but not implanted with the Braive™ GMS due to the investigator's discretion. If this occurs, it shall be documented on a study deviation eCRF, including the rationale for not implanting the device and the study exit form will be completed in the eCRF system.

9.1.4. Discharge Assessment

The following information will be collected at the discharge assessment (at the time of hospital discharge):

- Physical Assessment (weight and height)
- Imaging (P/A and lateral X-rays)
- Radiographic assessments as per standard of care
- Neurological Status
- Adverse events and/or device deficiencies
- Study Deviations

9.1.5. Post-operative Assessment at 3, 6, 12, 18, 24 months and annually

The following information will be collected at 3-month, 6-month, 12-month, 18-month, 24-month post-operative visits and annually thereafter until skeletal maturity is reached:

- Physical Assessment (weight and height)
- SRS-22
- Imaging (PA and lateral X-rays)
- Radiographic assessments as per standard of care
- Adverse Events and/or device deficiencies
- Study Deviations

Medtronic Controlled Information

- Risser score (only required on and after 24 months)

9.2. Diagnostic Tests

The following medical imaging and laboratory assessments will be performed during the study.

9.2.1. Spirometry Assessment

Pulmonary function will be assessed at the pre-operative visit by collecting the following parameters:

- Forced Vital Capacity (FVC)
- Forced Expiratory Volume in one second (FEV1)
- Total Lung Capacity

9.2.2. Radiographic Assessment

Images collected will be evaluated by investigators for adverse event, device deficiency and additional secondary endpoints analysis. The following series of radiographs will be obtained per the Schedule of events.

- P/A Thoracolumbar Spine
- Neutral Lateral Thoracolumbar Spine
- P/A Right Lateral Bending Spine
- P/A Left Lateral Bending Spine
- P/A Left Hand
- StealthStation DICOM
- Intraoperative AP fluoroscopy

With the early enrolment stop, the decision was taken to use Core Lab assessments for patient eligibility assessment only. The remaining radiographic assessments will be performed by the study sites as per their standard of care. For relevant endpoints, study site will follow the Radiographic Evaluation Protocol for radiographic measurements. The Radiographic Evaluation Protocol is maintained separate from this CIP.

9.2.3. O-Arm™ Imaging System and Stealth Station Image Acquisition

Sites using image guidance in the procedure workflow may have imaging collected from Medtronic O-Arm Surgical Imaging System and Medtronic StealthStation. Images being obtained off the systems are from the procedure workflow following the Navigated Surgical Technique. The StealthStation DICOM will be obtained per the Schedule of Events for potential future use:

- To confirm the post-operative position of the Braive™ GMS System
- To verify the amount of correction achieved by the Braive™ GMS System during surgery
- To further develop the Braive™ GMS System and the surgical technique
- To develop future capabilities that improve O-arm™ Imaging System image quality, reduce X-ray dose

Medtronic Controlled Information

to the patient, and aid in the development of segmentation and other algorithms/features that can enhance a surgeon or radiologist's decision-making ability

- To develop future capabilities that improve algorithmic segmentation of anatomy and aid in new development or enhancement of current surgical planning features for Medtronic platforms (i.e., StealthStation™, Mazor X™ Stealth Edition, BraiveSim)
- To validate a patient-specific computer modeling software that will generate patient-specific simulations of growth and curvature over time (only applicable for those patients that provide separate consent for this since the data may need to be shared with an external vendor)

9.2.4. Intraoperative Image Acquisition

For sites that are not using image guidance, intraoperative AP fluoroscopy images will be collected before and after implantation of the Braive™ system during surgery to:

- Confirm the post-operative position of the Braive™ System
- To verify the amount of correction achieved by the Braive™ GMS System during surgery
- Further development of the Braive™ GMS System and the surgical technique
- To validate a patient-specific computer modeling software that will generate patient-specific simulations of growth and curvature over time (only applicable for those patients that provide separate consent for this since the data may need to be shared with an external vendor)

9.2.5. Risser Score

Risser Score will be assessed by the investigator to evaluate the skeletal maturity of the subject in accordance with the following definitions:

Grade 0: No iliac apophysis visible.

Grade 1: Initial appearance of ossification of the iliac apophysis.

Grade 2: Migration halfway across the top of the iliac wing.

Grade 3: Three-fourths of the distance.

Grade 4: Ossification crossing the iliac wing, but not fused to the ilium.

Grade 5: Complete ossification of the iliac apophysis with fusion to the ilium.

When grade 5 is reached on or after 24-month follow up visit, subject will be exited from the study.

9.2.6. Pregnancy Testing

All subjects of childbearing potential must receive a pregnancy test (urine or serum test) within 72 hours prior to the study surgery. If the result of the pregnancy test is positive, the subject will be withdrawn from the study prior to surgery and will not receive the study treatment.

9.3. Subject Consent

The informed consent process in this study will be conducted in compliance with the Informed Consent regulations in 21 CFR 50 (US only), Declaration of Helsinki 2013, ISO 14155:2020 and national/local data protection laws and regulations. All subjects and/or parents/legal guardians for this study will be provided with an Informed Consent/Assent (as applicable) describing this study and providing sufficient information to make an informed decision about the subjects' participation in this study. The Informed Consent and Assent templates will be submitted with the protocol for review and approval by an IRB/EC/REB and the Regulatory Authorities, where applicable.

The investigator or authorized designee must obtain written informed consent/assent from the subject and/or parent(s)/legal guardian before any clinical study related activity takes place. Prior to entering the study, the investigator, or his/her designee, will inform all potential subjects and parent(s)/legal guardian about all aspects of the study (e.g., the purpose and nature of the study, procedures, potential risks, follow-up schedule, and expected duration).

All items addressed in the Informed Consent Form/Assent Form must be explained. The language used shall be as non-technical as possible and must be understandable to the subject.

The investigator or designee will discuss the foreseeable risks as well as potential benefits that may result from participating in the study and the available alternative therapies.

The subject and/or parent(s)/legal guardian must have ample time and opportunity to read and understand the Informed Consent Form/Assent Form, to inquire about details of the clinical study, and to decide whether to participate in the clinical study. All questions about the clinical study should be answered to the satisfaction of the subject and/or the parent(s)/legal guardian.

Neither the investigator, nor the investigation site staff shall coerce or unduly influence a subject and/or parent(s)/legal guardian to participate or to continue to participate in the clinical study. The informed consent/assent process shall not waive or appear to waive the subject's rights. Subjects and/or parent(s)/legal guardian will be informed by the investigator or designee that they are free to refuse to participate in the study, and if they choose to participate, that they may withdraw from the study at any time without compromising further medical care. In addition, subjects and/or parent(s)/legal guardian will be informed that the investigator may terminate their participation at any time without their consent. Written informed consent/assent will be obtained prior to subject enrollment and before any study-specific procedures are initiated.

Whenever new information becomes available that may be relevant to the subject's confirmed participation in the clinical study, Medtronic will revise the written Informed Consent Form/Assent Form and inform the investigators. The revised information will be sent to the investigator for approval or

Medtronic Controlled Information

notification by the IRB/EC/REB and the Regulatory Authorities, where applicable. An approved copy of this information must be provided to the participating subjects and/or parent or legal guardian, and the informed consent process as described above needs to be repeated. The investigator should inform the subject in a timely manner whenever new information becomes available that may be relevant to the subject's confirmed participation in the clinical study.

The investigator or designee will also determine that the subject/parent(s)/legal guardian can read, comprehend and make a decision regarding study participation of the subject (as applicable).

The original, signed and dated ICF/Assent Form must be retained in the subject's study records. The informed consent process must be documented in the subject's medical records and signed copies of the ICF/Assent Form will be provided to the subject and/or parent(s)/legal guardian. The date the subject and/or parent(s)/legal guardian signed the Informed Consent Form and data protection authorization (if applicable), and/or Assent must be documented in the subject's medical records.

9.4. Assessment of Safety

The criteria outlined in this section will be used to evaluate each subject before, during, and after surgery to determine the safety associated with the subject's treatment and study procedures. The safety of the Braive™ GMS will be assessed by evaluating the nature and frequency of AEs and additional surgical procedures (such as reoperations, revisions, or removals) and overcorrection.

9.4.1. Primary Safety Endpoint

The safety endpoint is any device-related adverse events up to 24 months. For this endpoint, the summary will be based on both Investigators and Medtronic relatedness assessment.

9.4.2. Secondary Safety Endpoint

The secondary safety endpoints are listed below:

- Procedure-related adverse events up to 24 months
- Secondary Spinal surgeries related to the original study device up to 24 months
- Device deficiency up to 24 months

For these endpoints, the summaries will be based on both Investigators and Medtronic relatedness assessment.

9.4.3. Adverse Events

Medtronic Controlled Information

All AEs will be collected (see section 11 for further details). AEs will be evaluated before, during and after surgery to determine the safety associated with the subject's treatment and study procedures.

The AEs will be classified according to the classification in Table 7: AE Definitions/Classifications.

The safety of the investigation will be assessed by evaluating the nature and frequency of AEs and subsequent spinal surgical procedures, as well as overcorrection, if applicable.

A steering committee and Medtronic medical advisor will monitor the safety of investigational treatment.

All adverse events will be reviewed by a Medtronic safety representative.

9.4.4. Neurological Status

Neurological status will be evaluated prior to the study treatment and at discharge. Neurological status can be performed at the investigator's discretion according to their standard of care at study follow up visits. Abnormalities should be reported as adverse event.

Neurological status is based on four types of measurements (sections): motor, sensory, reflexes, and straight leg raising. Each of the sections is comprised of a number of elements. Following scales will be used to evaluate neurological status: reflexes (0 = Absent, 1= Hypo-reflexia, 2 = Normal, 3 = Hyper-reflexia), sensory function (Light Touch T1 to S1, 1=Absent, 2=Impaired, 3=Normal), motor function (using 0-5 scores whereas 0= Total Paralysis, 1 = Palpable or Visible Contraction, 2 = Active Movement, Gravity Eliminated, 3 = Active Movement, Against Gravity, 4 = Active Movement, Against Some Resistance and 5 = Active Movement, Against Full Resistance (full strength) and straight leg raise (1 = positive, patient experiences radiating leg pain below the knee on elevating the leg between 15 and 70 degrees with the knee extended, 2 = negative, no pain is experienced on elevating the leg between 15 and 70 degrees with the knee extended).

Neurological change will be defined as deteriorate, maintenance or improvement in all sections (motor, sensory, reflex, and straight leg raising) between baseline and discharge. In order for a section to be considered a success, each element in the section must remain the same or improve from the time of the baseline evaluation to discharge. Therefore, if any one or more elements in any section does not stay the same or improve, then a patient will not be considered a success for neurological status. Note: For reflex, a change from Hypo-reflexia to Hyper-reflexia or a change from Hyper-reflexia to Hypo-reflexia is considered as maintained.

9.4.5. Overcorrection

When the growth modulation occurs at a relatively rapid rate, the spine may grow past a corrected (e.g., 0 degree or neutral) alignment. This phenomenon is termed overcorrection as it represents an overshoot of the desired clinical account of a 0 degree Cobb angle. A negative main thoracic Cobb angle indicates reversal of the curve, i.e., from right-sided to left-sided curve.

The risk of overcorrection is mitigated by the following:

- Limiting enrollment to subjects with a Sanders Score equal or greater than 2 to allow sufficient growth time for the Braive™ GMS to correct the curve without allowing extra time for overcorrection.
- Requiring investigators to review the educational tool and to follow the surgical technique.
- The risk reduction is achievable by understanding the potential for a rapid growth spurt (e.g., Sanders score) and the surgeon's control to avoid excessive compression with the Braid (e.g., surgical technique). Prior to skeletal maturity, clinically significant overcorrection of the curve can be treated by removing the Braid or releasing tension by cutting the Braid, which will allow increased growth of the vertebrae on the operated side and may reduce the overcorrection. After skeletal maturity, clinically significant overcorrection of the curve can be treated by fusion surgery, which is the standard of care for skeletally mature patients who have failed bracing and were not treated with vertebral body tether. The potential sequelae for overcorrection are the same as those for scoliosis; however, the degree of overcorrection curvature is likely to be less than the degree of curvature at baseline. Potential complications include: cosmetic such as uneven shoulders, one hip or rib cage prominent, and body tilted to one side, low back pain, lower self-esteem, decreased social functioning, depression, persistent pain if there is wear and tear of the spine bones, spinal infection after surgery, spine or nerve damage from curve or spinal surgery, and lung and heart problems (in severe scoliosis with curves > 70 degrees).

If overcorrection occurs, it will be at the discretion of the physician, in consultation with the patient and family, to determine if surgical intervention is necessary. Overcorrection is considered clinically significant if it is greater than 20 degrees and/or if it requires a secondary spinal surgery classified as treatment failure and will be considered a device-related adverse event.

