Moderate (Grade 2): Minimal, local or noninvasive intervention indicated; limited age appropriate instrumental activities of daily living (preparing meals, shopping, using the phone, managing

money, etc.).

Severe (Grade 3): Severe or medically significant but not immediately life-threatening; hospitalization or prolongation of hospitalization indicated; disabling; limiting age appropriate self-care activities of daily living (bathing, dressing and undressing, feeding self, toileting, taking medications, and not bedridden).

Life Threatening (Grade 4): Life threatening consequences; urgent intervention indicated; death.

SUBSEQUENT SPINAL SURGICAL INTERVENTION

Subsequent spinal surgical interventions will be classified using the following definitions, based on the description provided:

- Revision is a procedure that adjusts, or in any way modifies or removes, *part* of the original implant configuration, with or without replacement of a component. A revision may also include adjusting the position of the original implant configuration. Revisions will be considered in two categories:
 - Preventive surgery: Any braid manipulations (e.g., cutting or loosening the braid). *Preventive surgery for overcorrection will not be considered a treatment failure*
 - Non-preventive surgery: The revision is the result of an adverse event, i.e., the initial positioning of the device contributed to the adverse event and must be repositioned, or additional instrumentation is added to the original implant configuration. *Non-preventive surgery will be considered as a treatment failure.*
- Removal is a procedure where *all* of the original system configuration is removed with or without replacement. *Removal surgery will be considered a treatment failure.*
- Reoperation is a surgical procedure at the study treatment level(s) that does not involve removal, modification, or addition of any components to the original system. Examples include debridement of a surgical wound, scar revision or evacuation of a hematoma. *These will not be considered a treatment failure.* Spinal fusion or extension of the fixation due to the progression of initial scoliosis *will be considered a treatment failure.*
- Other is any other subsequent spinal surgical procedure not classified as a revision, removal or reoperation. Examples include spinal surgery not at the study treatment level(s) such as microdiscectomy or hernia repair.

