13.3. Primary Analysis Population

The primary analysis population will include all subjects who are enrolled and undergo the Braive™ GMS surgical procedure. The primary dataset will be used for all the analyses. For subjects who are treatment failures, the last postoperative observation before the first treatment failure will be carried forward for all additional secondary endpoints and neurological status. No imputation for missing data will be made for other subjects.

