13.4. Analyses for Additional Secondary Endpoints

All additional secondary endpoints are listed in the section 5.2.3. For the additional secondary endpoints related to the change from the baseline (pre-op or post-op baseline for instrumented Cobb angle), when the distribution of data is approximately normally distributed, the changes from baseline will be tested using a paired-sample t-test. When the distribution of the data is severely non-normal, a Wilcoxon signed-rank test may be used in place of the paired t-test. In addition, the descriptive statistics including but not limited to mean, standard deviation, median, minimum and maximum will be calculated and presented. For “Status of return to full activity within 3 months per SRS-22”, the number and percentage of subjects returned to full activity within 3 months will be calculated and presented.

Additional analysis will be performed by comparing the postoperative measurements at follow up visits with the measurements at immediate post-op.

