The purpose of this study was to establish probable benefit and evaluate the safety and preliminary effectiveness of the Braive™ GMS when used in the treatment of JIS and AIS.

In March 2023, Medtronic made the decision to discontinue the BRAIVE program. All sites, therefore, have been notified to discontinue study enrollment and there are no plans at this time to utilize collected data to obtain Humanitarian Device Exemption (HDE) approval.

This decision is not associated with any safety or efficacy observations from the study, and the study has not received stopping recommendations from the Data Monitoring Committee.

5. Investigation Plan

This is a prospective, multi-center, single-arm study of the Medtronic Braive™ GMS. As all subjects will have failed conservative care as per investigator's assessment, they will serve as their own controls. The baseline measurements will be collected prior to implantation of the device and compared against the measurements collected postoperatively. Data will be evaluated mainly for safety. Each subject will be followed until skeletally mature.

Clinical assessments will be completed at baseline (preoperatively), during surgery, and postoperatively at discharge, 3 months, 6 months, 12 months, 18 months, and 24 months, and then annually until subjects reach skeletal maturity (defined as Risser 5 as assessed by the investigator).

6. Determination of Sample Size

This study was designed to show that the investigational device can be used to obtain a statistically significant improvement (>0) in the Cobb angle. The initial sample size required to demonstrate a statistically significant improvement of Cobb angle at 24 months as compared to that in the preoperative visit is 24. Medtronic planned to treat 25 subjects (refer to SAP V5.0 for detail). Due to the decision to stop the enrollment early, the sample size is 10 at the time of this decision.

7. Statistical Methods

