7.1.3 Analysis Sets

7.1.3.1 Primary Analysis Population

The primary analysis population will include all subjects who are enrolled and undergo the Braive™ GMS surgical procedure. The primary dataset will be used for all the analyses. For subjects who are treatment failures, the last postoperative observation before the first treatment failure will be carried forward for analysis of additional secondary endpoints (see section 7.9.1).

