7.9.1 Analysis for Additional Secondary Endpoints

Additional secondary endpoints in addition to the secondary safety endpoints outlined in the section 7.10.2 are listed below:

- Change from baseline in main thoracic Cobb angle at all available postoperative time points
- Change from baseline in proximal thoracic Cobb angle at all available postoperative timepoints
- Change from baseline in thoracolumbar/lumbar Cobb angle at all available postoperative timepoints
- Change from post-op baseline in Instrumented Cobb Angle at all available postoperative time points
- Change from baseline in thoracic kyphosis at all available postoperative timepoints
- Change from baseline in Lumbar Lordosis at all available postoperative timepoints
- Change from baseline in coronal balance at all available postoperative timepoints
- Change from baseline in Sagittal Balance at all available postoperative timepoints
- Change from baseline in total vertical thoracic spine height (T1- T12) at all available postoperative timepoints
- Change from baseline in total vertical spine height (T1-S1) at all available postoperative timepoints
- Change from baseline in Scoliosis Research Society-22 Patient Questionnaire (SRS-22) at all available postoperative timepoints
- Status of return to full activity within 3 months per SRS-22

For the additional secondary endpoints related to the change from the baseline, when the distribution of data is approximately normally distributed, the change from baseline will be tested using a paired-

sample t-test. When the distribution of the data is non-normal, a Wilcoxon signed-rank test may be used in place of the paired t-test. In addition, the descriptive statistics including but not limited to mean, standard deviation, median, minimum and maximum will be calculated and presented. For “Status of return to full activity within 3 months per SRS-22”, the number and percentage of subjects returned to full activity within 3 months will be calculated and presented.

Additional analysis will be performed by comparing the postoperative measurements at follow-up visits with the measurements at immediate post-op.

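### The plain Cobb change score counts a curve that passes 0 degrees as more correction than a straight spine, and overcorrection has no summary of its own.

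*Protocol*

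**What the plan says.** **Sign and target.** Protocol section 9.4.5 describes overcorrection as overshoot of a 0-degree Cobb angle and states: "A negative main thoracic Cobb angle indicates reversal of the curve". Overcorrection is clinically significant above 20 degrees and/or when it needs a secondary surgery classified as a treatment failure. It is then a device-related adverse event (AE). Section 10.2.3 calls overcorrection the main risk of the procedure.

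**Endpoint and test.** SAP section 7.9.1 lists "Change from baseline in main thoracic Cobb angle at all available postoperative time points". Protocol section 13.4 adds that "the changes from baseline will be tested using a paired-sample t-test", with a signed-rank test as the alternative. Neither section gives a rule for angles past 0. SAP section 6 says that the study was designed "to obtain a statistically significant improvement (>0) in the Cobb angle".

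**Treatment failures.** Protocol section 13.3: "the last postoperative observation before the first treatment failure will be carried forward for all additional secondary endpoints". SAP section 7.1.3.1 agrees: "the last postoperative observation before the first treatment failure will be carried forward for analysis of additional secondary endpoints". Protocol section 13.5 and SAP section 7.4, however, say that every analysis uses observed data without imputation. In protocol section 11.1, Table 7: "Removal surgery will be considered a treatment failure", but "Preventive surgery for overcorrection will not be considered a treatment failure".

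**Safety reporting.** Protocol sections 9.4 and 9.4.3 name overcorrection among the things by which safety is assessed. Protocol section 13 and SAP sections 7.9 and 7.10 contain no item with that name.

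**The concern.** The change score has no turning point at 0. Between a 45-degree curve and a straight spine, a lower angle is better. Past 0 the spine is curving the other way, and section 9.4.5 says the possible consequences are the same as those of scoliosis. The score nevertheless keeps rising. A subject who goes from 45 to -25 degrees shows 70 degrees of reduction, and one who ends straight shows 45.

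The main thoracic Cobb angle is the outcome on which the study was sized, and section 15.9 says that results will be released on a public registry. A reader will take a larger mean reduction as a better result. With 10 subjects, one reversed curve can move that mean by several degrees in the favourable direction, and nothing in the planned Cobb tables need reveal it.

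**Working it through.** **Inputs.** Treated subjects n = 10 (protocol section 9.1.1). Entry angle 30 to 60 degrees (section 8.3). Sign convention and 20-degree threshold (section 9.4.5). Overcorrection in earlier tethering series 13/116 (section 4.1). All individual angles below are assumed.

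**1. The protocol's own figure.** 13/116 = 0.1121, which reproduces the stated 11.2% (exact 95% interval 6.1% to 18.4%). At that rate the expected number in 10 subjects is 10 × 0.1121 = 1.1 (0.6 to 1.8). The chance of at least one is 1 − (1 − 0.1121)^10 = 69.5% (46.7% to 86.9%). Those series used other or unspecified tethers and give no degrees, so this is the chance of any overcorrection, not of one above 20 degrees.

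**2. Effect of one reversal on the mean.** Let b be the baseline angle and −d the follow-up angle.

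- Signed reduction: b − (−d) = b + d
- Reduction if the spine were straight: b
- Reduction in distance from 0: |b| − |−d| = b − d

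The signed score exceeds the straight-spine score by d and the distance score by 2d. Divided by n = 10:

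| d (degrees) | Added to mean v straight spine (d/10) | Added to mean v distance from 0 (2d/10) |
|---|---|---|
| 10 | 1.0 | 2.0 |
| 20 | 2.0 | 4.0 |
| 25 | 2.5 | 5.0 |
| 30 | 3.0 | 6.0 |

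**3. Example with a test.** All baselines are 45. Nine subjects end at 10, 14, 16, 18, 20, 22, 24, 26 and 30 (sum 180), so their reductions total 9 × 45 − 180 = 225. The tenth varies:

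| Tenth subject | Scoring | Mean reduction | SD | Absolute t |
|---|---|---|---|---|
| 0 | either | (225 + 45)/10 = 27.0 | 8.6 | 9.88 |
| -25 | signed | (225 + 70)/10 = 29.5 | 15.4 | 6.06 |
| -25 | distance from 0 | (225 + 20)/10 = 24.5 | 6.1 | 12.71 |

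The mean moves up but the t statistic falls, because the SD grows. The effect is on the estimate, not on significance.

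**4. Would the planned minimum and maximum reveal it?** A reduction proves reversal on its own only if it exceeds the largest possible baseline, 60 degrees. The overcorrection must then exceed 60 − b: 30 degrees from a baseline of 30, 20 from 40, 15 from 45. Below that the change is ambiguous. A 50-degree reduction is a residual curve of 60 − 50 = 10 degrees in one subject and a reversal of 30 − 50 = −20 in another.

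**5. Carry-forward.** Section 10.4 includes device removal among the possible treatments of clinically significant overcorrection, and removal of the whole system is a treatment failure. The last angle before it, if reversed, is then carried forward. Section 9.4.6.1 limits later imaging to qualitative assessment, so no later angle replaces it. Cutting or loosening the braid preventively for overcorrection is not a failure, and those subjects keep their observed angles. The documents give no frequency for either path.

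**The case against.** A reader might infer that overcorrection is counted nowhere. The documents do not support that. Clinically significant overcorrection is a device-related AE by definition. It therefore enters the primary endpoint (protocol section 13.6.1, SAP section 7.10.1), the AE listings and summaries (protocol section 13.6.3, SAP section 7.10.3) and the AE narratives (protocol section 13.6.3). Secondary surgeries are counted by type, with preventive revisions separate (protocol sections 9.4.6.1 and 13.6.5, SAP section 7.10.4). What remains is narrower. No summary is labelled overcorrection, and a reversal of 20 degrees or less without failure-classified surgery, including one treated by preventive braid surgery, lies outside the section 9.4.5 definition. It can still be reported as an AE on ordinary grounds, but the definition does not require it.

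A reader might also infer that carry-forward routinely locks in reversed angles. It does so only after a failure-classified surgery, and only if sections 13.3 and 7.1.3.1 prevail over the no-imputation statements.

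Three further points are fair. No passage states that signed values enter the change score. The improvement wording belongs to the superseded sample-size rationale, and the endpoint is now one of 12 additional secondary endpoints in an analysis that SAP section 7.5 calls descriptive. A signed mean is also an unbiased estimate of signed change, and distance from 0 has its own blind spot, since it scores -20 and +20 alike. These points limit the weight of the concern, and the last is why both measures should be shown beside the angle itself. They do not remove it: section 9.4.5 gives the only convention in the documents. If sites instead recorded unsigned angles, a reversal to -25 would look like a residual curve of 25, which also needs a stated rule.

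**Conclusion.** The concern holds in a limited form. Under the documents' only sign convention, the Cobb change score ranks a reversed curve above a straight spine, contrary to the 0-degree target in section 9.4.5. One reversal of d degrees among 10 subjects adds d/10 to the mean reduction relative to a straight spine and 2d/10 relative to the change in distance from 0. In the assumed example that is 2.5 and 5.0 degrees.

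This rests on two assumptions: that signed angles are analysed, which the separate Radiographic Evaluation Protocol could confirm or refute, and that the size of any reversal is in the range shown, for which the documents give no data. It does not imply that the primary safety rate misses clinically significant cases, or that reversals create statistical significance. The carry-forward element is conditional and cannot be settled until the conflicting sections are reconciled. The lack of a dedicated overcorrection summary is a gap against protocol sections 9.4 and 9.4.3.

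**What to change.** Update the SAP only:

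- **Section 7.9.1.** Beside the signed change, report the main thoracic Cobb angle itself at each visit and the change in distance from 0 degrees (absolute baseline minus absolute follow-up). State that angles are analysed with sign and that change past 0 is not read as further improvement.
- **Section 7.10.** Add a count and listing by visit of subjects with a negative main thoracic angle, any and more than 20 degrees. Show any secondary surgery and whether the case was reported as a device-related AE.
- **Sections 7.1.3.1 and 7.4**, with protocol sections 13.3 and 13.5. Reconcile carry-forward with the no-imputation statements. If carry-forward is kept, flag every carried-forward negative angle in the listing.

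The cost is one derived variable and one listing. Radiographic assessments are already scheduled at discharge and every follow-up visit, so no new data are needed if the sign is recorded. The reported mean correction may be smaller. Definitions, assessors' relatedness calls and patient care stay unchanged.
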